8.1.5 Analysis of Safety Data

Safety Endpoints

1. Number of participants with treatment-emergent AEs (defined as any AE occurring or worsening following treatment), summarised by system organ class (SOC) and preferred term (PT)

Note: Occurrence of ISRs will be included.

- 2. Mean changes in vital signs, triplicate 12-lead ECGs and laboratory data parameters at each visit during the 168-day treatment period, compared to baseline
- 3. Continuous 24 hour 12-lead Holter ECG (subset of 30 Group 2 subjects only)
- 4. Percentage of participants with ISRs at each visit during the 168-day treatment period *Note:* Photography of injections sites with visible injection site reactions will be performed at each visit, and ISRs will be scored based on a specific scoring matrix

The treatment-emergent AEs (defined as any AE occurring or worsening with the same date or later than that of the first application of study treatment) will be coded using the most recent version of the Medical Dictionary for Regulatory Activities (MedDRA) available at the study start date. This version will be used throughout the entire study. Updates to MedDRA will not be applied afterwards. Frequency tables for the preferred terms will be compiled based on participants experiencing an AE and on the number of AEs. These frequency tables will take the SOC into consideration.

All reported AEs will be listed and ISRs will be summarised.

The vital sign, triplicate 12-lead ECG, and laboratory data parameters will be presented using descriptive statistics and shift-tables with respect to normal ranges for each visit including changes from baseline.

Concomitant diseases and medical history will also be coded using MedDRA. These data will be presented using frequency tables by SOC and PT.

Previous medication and concomitant medication will be coded using the Anatomical Therapeutic Chemical Classification (ATC) dictionary. Frequency tables will be compiled based on the coding for the medication.

8.1.6 **Missing Data**

Missing efficacy data will not be replaced in general.

If a laboratory reports concentrations as unquantifiable (too low), the value will be set to 0. Values for samples that are not technically evaluable will be set to missing.

In case a start date for an AE is missing or incomplete, so that it is not possible to evaluate if it has occurred pre- or post-treatment, this AE will be classified conservatively as treatment-emergent. More information on missing data imputation will be described in the SAP.

8.1.7 **Multicentre Study**

This study will be performed as a multicentre study. Count and proportion of participants achieving castration level within the first 28 days, and participants maintaining castration over the 168-day treatment period will be stratified by site. No other risks are expected.

8.1.8 Participant Data Listings

All recorded data will be presented in-participant data listings.

8.1.9 Deviations from the Planned Statistical Analysis

Any deviations from the planned statistical analysis have to be discussed in the final study report and should be defined in the SAP.

Any deviations from the original SAP should be described and justified in the final study report.

8.1.10 Interim Analysis

After completion of Stage 1, i.e. after all participants have completed the visit at Day 28 and their T concentration levels are available, an analysis of the primary efficacy parameter will be performed analysing the number and proportion of participants reaching castration level by Day 28 with the loading dose of teverelix TFA.

The study will proceed during the analysis and all other efficacy, safety and demographic parameters will be evaluated at the end of the study (full analysis, Stage 2).

8.1.11 Software used for Statistical Analysis

The SAS® software version 9.2 (SAS® Institute) or higher will be used for the statistical analysis and for the reporting of this study. PK/PD analyses will be performed with Phoenix® WinNonlin® Version 6.3 or higher (Certara L.P).

8.1.12 **Determination of Sample Size**

Initially, since no confirmatory analyses were planned, no sample size calculations were performed. A total of 24 participants was deemed sufficient for 1 treatment group to obtain at least 20 evaluable participants (Day 168 visit completed).

Subsequently the Sponsor undertook a formal sample size calculation so that the Group 2 data could be used to support the dose selection for future Phase 3 clinical trials.

A sample size of 60 has been chosen on clinical grounds. This number gives good power to detect a minimum proportion of 90% subjects achieving castration with central lab serum T <0.5 ng/mL or 1.73 nmol/L at Day 28 from the per protocol population. It is based on the null hypothesis that the true response rate is 74.5%, the average response rate in previous Teverelix trials not achieving 90% response rate. This is tested using a two-sided test with a 5% alpha level against the alternative hypothesis that the response rate is 90%, the minimally clinically relevant response rate. Based on this, fifty participants give power of 80%. Assuming a dropout rate of 16%, sixty patients are recommended.

Sixty patients will ensure acceptable precision for justification for further analysis of this regimen in Phase 3. A true 90% response rate in this instance would give a confidence interval of (79,96) and if 10 subjects drop out, and interval of (78,97). A true 95% response rate with 60 participants would give a confidence interval of (86,99) and if 10 subjects drop out, an interval of (85,99).

8.2 **Data Management**

Data management will be performed using Oracle Clinical Version 3.3 or later running on 2 Microsoft Windows NT servers. Details will be defined in the data management manual, which will be signed by the Sponsor and the Clinical Research Organisation (CRO) prior to start of the data entry.

9 Data Handling and Data Quality Assurance

9.1 **Data Management**

Data will be captured using the eCRF provided by the designated CRO. The eCRF is specifically designed to meet the data recording requirements of the clinical study protocol. Only the investigator and his/her authorised staff who are trained appropriately on the eCRF system are allowed to fill in the eCRFs or to make corrections, and will have access to the data or may change data (however this access will be granted without the possibility to delete the original entries). After completion, each eCRF will be electronically signed and dated by the investigator. Central laboratory test results will be imported automatically into the eCRF. The overall procedures for quality assurance of clinical study data are described in the respective standard operating procedures (SOPs) of the CRO. A document describing the functional specification will be prepared by the CRO in cooperation with the eCRF provider and will be approved by the Sponsor prior to the start of the study. This functional specification will describe in detail the structure and functionality of the eCRF. In addition, the CRO will prepare a data management plan to describe the procedures and processes of data collection and data coding.

Electronic validation of the data entered in the eCRFs will take place (e.g. check of ranges, consistency, and plausibility). All plausibility checks will be defined in the data validation plan to be approved by the Sponsor. Additionally, the eCRFs will be reviewed by qualified data management and medically qualified personnel for completeness, consistency, and plausibility. Any data anomalies will be communicated to the site(s) for clarification/resolution (data query). Procedures of data entry and correction will be tracked and appropriately documented in the audit trail of the eCRF.

9.2 **Documentation**

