alternative treatment option will be tested: 180 mg each of teverelix TFA, given IM and SC, followed by SC injections of 180 mg of teverelix TFA every 6 weeks thereafter, for a total duration of 168 days. As this is a Phase 2 study to evaluate the dosage and effectiveness of teverelix TFA in the suppression and maintenance of serum T concentrations below castration levels, an open-label, non-controlled study design has been chosen.

4 Selection of Study Population

In this study, approximately 24 participants from Group 1, or 60 participants from Group 2 will be recruited from 7 up to study centres in Lithuania and potentially Netherlands and/or Belgium in order to provide a sample size of 20 participants from Group 1, or 50 participants from Group 2. These participants will comprise the per-protocol (PP) analysis set for evaluation of treatment response at Day 28 and throughout the study up to Day 168. As soon as this number of enrolled participants is reached, no more participants will be recruited. Enrolled participants who cannot be analysed in the PP analysis set will not be replaced. The participants for this study will be recruited from inpatient/outpatient departments of clinics/hospitals and/or general practitioners/specialists. If inpatients are included in the study, they will receive further treatment as inpatients.

4.1 **Participant Inclusion Criteria**

The participant is allowed to participate in the study if ALL of the following criteria are fulfilled:

- 1. Is male, aged \leq 85 years (\geq 18 years) at the beginning of the treatment period (Day 0)
- 2. Has histologically proven advanced adenocarcinoma of the prostate (metastatic or non-metastatic hormone-sensitive non-curative), suitable for ADT
- 3. Is treatment naïve for any of the following:
 - a. GnRH analogues
 - b. Androgen receptor antagonists, or
 - c. Androgen synthesis inhibitors (e.g. abiraterone)
- 4. Agrees to practice contraception during the entire study treatment period and for 3 months after the last dose of IMP is administered:
 - a. Either by using double barrier contraception,
 - b. or, is truly sexually abstinent, when this is in line with the preferred and usual lifestyle of the participant

Note: Periodic abstinence [e.g. calendar, ovulation, symptothermal, postovulation methods for the female partner with childbearing potential] and withdrawal are not acceptable methods of contraception.

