## 1. Introduction

This statistical analysis plan (SAP) is based on protocol ANT-1111-02 Version 5.0 dated 31 May 2022. The SAP contains a complete and detailed specification of the statistical analyses.

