### 5.2 Hypotheses and Decision Rules

The approach for testing the hypothesis, if any, will solely rely on utilizing confidence intervals.

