### 6.8.1 Primary Efficacy Analysis

Proportion of participants achieving castration level with serum T <0.5 ng/mL or 1.73 nmol/L at Day 28.

Descriptive statistics, including proportion, Clopper-Pearson confidence interval (CI), and absolute frequencies will be calculated

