## 7. Changes to the Planned Analyses

### 7.1 Changes to the Analyses Described in the Study Protocol and Protocol Amendments

Changes were made to the analysis definitions related to "Mean time to" events, which are now labelled as "Time to" events and will not contain the mean. This was changed due to the decision to use Kaplan-Meier methods of analyses for these, where the mean is not a suitable output in the presence of censoring.

After discussion with the FDA, a new Supplementary FDA Recommended Efficacy Analyses was added to the SAP.

The following analyses were also added:

PSA:

- PSA level at each visit
- Confirmed PSA Response Rate - defined as > 50% reduction in PSA from baseline at Day 14 followed with confirmation at Day 28
- PSA response rate at Day 28

FSH:

- FSH Level at each visit
- Percent Change From Baseline In Serum Concentrations Of FSH

LH:

- LH Level at each visit
- Percent Change From Baseline In Serum Concentrations Of Luteinizing Hormone

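### The 80% power claimed for 50 evaluable Group 2 participants is 77% under the exact interval the SAP plans, and the SAP never names the 74.5% null

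*Protocol*

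**What the plan says.** Protocol 8.1.12 gives a formal calculation for Group 2, made so that its data could support dose selection for Phase 3. On the null it says: "It is based on the null hypothesis that the true response rate is 74.5" per cent. The alternative is 90%, the test is two-sided at 5%, and the population is per protocol (PP). It concludes "Based on this, fifty participants give power of 80" per cent, and enrols 60 to allow for 16% dropout. No test or formula is named.

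The SAP handles inference differently. SAP 5.2 reads in full: "The approach for testing the hypothesis, if any, will solely rely on utilizing confidence intervals". For the primary endpoint SAP 6.8.1 says "Descriptive statistics, including proportion, Clopper-Pearson confidence interval (CI), and absolute frequencies will be calculated", and SAP 6.8 supplies code for the exact interval. Neither gives a confidence level for this proportion, a null value or a success rule. The rate 74.5% appears nowhere in the SAP; its only reference rate is 90% (SAP 2.2.1 and 6.8).

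Three further statements bear on this. SAP 1 claims: "The SAP contains a complete and detailed specification of the statistical analyses". Protocol 8.1.9 requires: "Any deviations from the planned statistical analysis have to be discussed in the final study report and should be defined in the SAP". SAP 7.1 lists the changes from the protocol, for example "After discussion with the FDA, a new Supplementary FDA Recommended Efficacy Analyses was added to the SAP", but says nothing about the 74.5% hypothesis.

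**The concern.** Two things do not fit together. First, the protocol's power belongs to an unnamed test, while the only inferential tool planned for the primary proportion is the exact interval. If that interval decides the matter, the power should be that of the interval.

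Second, the protocol says a hypothesis is tested, but the SAP leaves open whether there is one and never gives its null value. An analyst working from the SAP would produce an interval with nothing to compare it with. The nearest candidate in the SAP is 90%, which is the alternative in the sample-size calculation and would answer a different question. Results of 43/50 and 44/50 fall on opposite sides of the protocol's null, and no SAP rule says so. In an open-label, single-arm study meant to inform Phase 3 dose selection, that comparison should be fixed in writing before the Day 28 results are analysed.

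The evaluable number is also open. Protocol section 4 says: "Enrolled participants who cannot be analysed in the PP analysis set will not be replaced". The power therefore depends on how many remain in the PP set.

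**Working it through.** **Inputs.** Null p0 = 0.745, alternative p1 = 0.90, two-sided alpha 0.05, n = 50 evaluable, 16% dropout, 60 enrolled (all Protocol 8.1.12). Interval: Clopper-Pearson (Protocol synopsis; SAP 6.8 and 6.8.1). Level: assumed 95%.

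**Support for the 95% level.** The protocol's own precision intervals reproduce as 95% Clopper-Pearson:
- 54/60 gives 79.5% to 96.2%; stated (79,96).
- 45/50 gives 78.2% to 96.7%; stated (78,97).
- 57/60 gives 86.1% to 99.0%; stated (86,99).
- 95% of 50 (47.5, not a whole count) gives 84.8% to 99.2%; stated (85,99).

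**Reproducing the stated 80%.** The usual normal approximation is

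power = Φ[(p1 − p0 − 1.96·√(p0(1−p0)/n)) / √(p1(1−p1)/n)].

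At n = 50, √(0.745×0.255/50) = 0.0616 and √(0.90×0.10/50) = 0.0424. Power = Φ[(0.155 − 1.96×0.0616)/0.0424] = Φ(0.806) = 79.0%. Solving the same formula for 80% gives n = 50.99, so 51. The stated figure reproduces to within rounding, and so does the dropout step: 50/0.84 = 59.5, rounded up to 60.

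**Power of the planned interval.** Reject the null when the lower 95% Clopper-Pearson limit exceeds 0.745.
- 43/50: lower limit 73.3%, does not exclude 74.5%.
- 44/50: lower limit 75.7%, excludes it.
- Upper-tail size: P(X ≥ 44 | n = 50, 0.745) = 0.0161.
- Power: P(X ≥ 44 | n = 50, 0.90) = 0.7702, so the chance of failing to exclude 74.5% is 23.0%, not 20%.
- At n = 60: 51/60 has lower limit 73.4% and 52/60 has 75.4%; size 0.0173, power 0.8584.

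**Would the score test give 80%?** With null standard error 0.0616, z = (0.86 − 0.745)/0.0616 = 1.87 at 43/50 and (0.88 − 0.745)/0.0616 = 2.19 at 44/50. It also first rejects at 44, so its true power at n = 50 is the same 77.0%.

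**Other evaluable numbers (Clopper-Pearson rule, true rate 90%).**

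| Evaluable n | Smallest count that rejects | Exact power |
|---|---|---|
| 47 | 42 | 67.1% |
| 48 | 42 | 80.0% |
| 49 | 43 | 78.5% |
| 50 | 44 | 77.0% |
| 51 | 45 | 75.5% |
| 52 | 46 | 73.9% |
| 53 | 46 | 84.4% |
| 54 | 47 | 83.2% |
| 55 | 48 | 82.0% |
| 56 | 49 | 80.7% |
| 57 | 50 | 79.3% |
| 58 | 50 | 87.9% |
| 59 | 51 | 86.9% |
| 60 | 52 | 85.8% |

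Between 50 and 60 evaluable, power ranges from 73.9% to 87.9% and is below 80% at 50, 51, 52 and 57. The choice of method also matters at some n: at 52 the score test first rejects at 45 (power 85.6%), against 46 (73.9%) for the exact interval.

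**The case against.** The best case for leaving this alone has four parts.

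- **The 80% is a conventional approximation and was never called exact.** This is true. The point is a mismatch of method, not a miscalculation.
- **The 3-point gap is largely discreteness.** Also true: power is 80.0% at 48 evaluable and lower at 50, and the rule's upper-tail size at 50 is 1.6% against a nominal 2.5%. The protocol says 60 was chosen on clinical grounds, and its precision argument is untouched. The gap would not change the design.
- **The null is prespecified in the protocol on which the SAP is based, and the protocol's own analysis text contains no test either.** This has some force. Protocol 8.1.3 names only endpoint and population, and the synopsis gives only the proportion and its interval, so the inconsistency lies partly inside the protocol. A careful reader could assemble the rule from both documents. But a SAP that claims completeness should not leave its one sized comparison to be inferred, especially when it says any testing is by interval and the only rate it mentions is 90%.
- **The powers assume that evaluability is unrelated to response.** This stands as a caveat. Participants with local testosterone above 2 ng/mL are withdrawn, and the PP set requires completing the study, so the PP rate need not equal the underlying rate. The protocol's power statement makes the same assumption, so the comparison of 80% with 77% is like with like.

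**Conclusion.** The concern holds. With 50 evaluable, the planned analysis has 77.0% power at a true 90% rate, not 80%; with 60 it has 85.8%. The SAP contains neither the 74.5% null nor a rule for it, and SAP 7.1 does not record its absence. The omission matters more than the 3 points of power, because it leaves the primary interval without a stated comparison.

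The result assumes a two-sided 95% Clopper-Pearson interval and a 90% response rate in the PP set, with evaluability unrelated to response. The 23% is the chance of failing to exclude 74.5%; it is not the chance of an observed rate below the 90% target. This should be corrected, but it does not undermine the sample size.

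**What to change.** In SAP 5.2 and 6.8.1, state that for Group 2 in the PP set the 74.5% null is rejected if the lower limit of the two-sided 95% Clopper-Pearson interval for the Day 28 rate is above 74.5%, whatever the evaluable number (for example at least 44/50 or 52/60). State that any comparison with 90% is descriptive. Give the power of that rule there: about 77% at 50 evaluable and 86% at 60. Restate Protocol 8.1.12 to match, naming the method.

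If no test is intended, record in SAP 7.1 that the hypothesis in Protocol 8.1.12 will not be tested.

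The cost is a few sentences in the SAP, with no change to enrolment or data collection. They should be in place before the Day 28 results are analysed, and in any case before database lock, after which SAP 7.2 allows no change to this version. Correcting Protocol 8.1.12 needs a formal amendment (Protocol 10.2), and can wait for the next one if the SAP carries the right figure. The only drawback is a slightly less favourable stated power.

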9.2.1 Pre-screening List and Participant Identification List

A screening log will be kept by the investigator, listing all participants screened for this study. Participants will be identified by initials and year of birth. The status of the participant, i.e. whether enrolled in this study or not, will be entered on the log.

All participants who have given informed consent to participate in the study – regardless of whether the participant has received any investigational product(s) or not – have to be entered on the participant identification list by the investigator, giving full name, initials, year of birth, and participant identification code. The participant identification list will be kept in the investigator's file.

9.2.2 Source Data and Participant Records

In this study, all collected data in the participant file are considered source data. All data reported in the eCRF must be supported by appropriately signed identified source documents.

9.2.3 Electronic Case Report Form

An appropriate eCRF in English will be developed by the CRO. An eCRF completion manual for the use of the electronic data capture system will be provided prior to the study start, and

investigators will be trained on how to enter all study-specific data into the eCRF. Investigators must enter the information required by the protocol into the eCRF and should complete the eCRF as soon as possible, but on the 3rd working day after a participant visit at the latest (or in case of on-site assessment results: within 3 working days after the on-site assessment). No questions must be left unanswered.

Note: All SAEs must be reported by the investigator immediately (within 24 hours) via the SAE form in the eCRF (see Section 6.3.7.4).

Monitors will review the eCRFs for completeness and accuracy, and instruct site personnel to make any required corrections or additions. The eCRFs are saved immediately after entering the data by the investigator. All eCRF data are stored in a central database at the eCRF provider while the study is ongoing and at the responsible CRO for final analysis after study completion.

After study completion, the study site will receive a CD/DVD with a compilation of the eCRF study data per site (electronic PDF files) for filing with its study documents. The Sponsor will receive electronic, bookmarked PDF files of individual eCRFs (including audit trail). The Sponsor will also receive a list of queries and SAE forms after database closure.

9.3 Direct Access to Source Data/Documents

Checking of eCRFs for completeness and clarity, and cross-checking with source documents will be required to monitor the progress of the study. The CRAs are entitled to compare eCRF entries with source data and to inform the investigator about errors and omissions. The investigator will provide direct access to source data/documents for the Sponsors designated representatives (CRAs and auditors) as well as IRB/IEC members and regulatory inspections. Regulatory authorities and/or the Sponsor's Clinical Quality Assurance Group may also carry out such source data checks and/or on-site audit inspections. They will be carried out giving due consideration to data protection and medical confidentiality. The investigator is to give the CRO and the Sponsor whatever support is necessary.

9.4 **Monitoring**

Monitoring will be done in accordance with the stipulations of Chapter 5.18 of the ICH GCP Guideline by Insuvia UAB CRAs.

During the course of the study, a CRA will make site visits to review protocol compliance, compare eCRFs and individual participants' medical records, assess drug accounting, and ensure that the study is being conducted according to pertinent regulatory requirements and the protocol. eCRF entries will be verified against source documentation in accordance with the applicable SOPs of the Sponsor/CRO. CRAs of the CRO will maintain confidentiality of the personal data of participants.

The investigator will allow the study monitor to make regular visits during the course of the study to:

- Verify that written informed consent was obtained prior to each participant's participation in the study
- Discuss any emergent problem
- Check the eCRFs for completeness and plausibility
- Review accountability, correct storage, and handling of the IMP
- Ensure that the study is being conducted according to pertinent regulatory requirements, ICH GCP E6(R2), and the protocol

A close-out visit will be performed upon the conclusion of the study site's participation in the study.

The Sponsor reserves the right to order special examinations of laboratory samples if there is any doubt concerning the validity of individual participant data or the accuracy of data generation at an investigational site.

9.5 **Quality Assurance**

Risk-based quality management will be implemented in this study based on the requirements of the Integrated Addendum of the Good Clinical Practice guideline ICH E6(R2). Aspects of risk-based quality management will be detailed in a risk management plan.

A member of the Sponsor's (or designated CRO's) quality assurance unit may conduct an audit at the study site to ensure compliance with the protocol, GCP, and the applicable regulatory requirements.

In addition, inspections by regulatory health authority representatives and IEC(s)/IRB(s) are possible. The investigator or his/her designee should notify the Sponsor immediately of any such inspection.

The investigator is expected to cooperate with such inspections and to discuss any findings with the auditor. The observations and findings of the auditor will be documented and the investigator will be informed of the audit outcome.

10 Ethical, Legal and Administrative Aspects

The study will be carried out in conformity with the ethical principles enunciated in the Declaration of Helsinki. The current valid version according to applicable national regulatory and legal requirements will be considered.

The study will also be carried out in accordance with the Integrated Addendum of the ICH Guideline on Good Clinical Practice E6(R2), the Regulation EU No. 536/2014, which will replace the EU Clinical Trial Directive 2001/20/EC, the Commission Directive 2005/28/EC (April 8, 2005), and all local laws, regulatory requirements, and guidelines applicable in the participating countries.

By signing the Investigator's Declaration, the investigator agrees to conduct the study as set out in this protocol and in accordance with the moral, ethical and scientific principles governing clinical research.

Signatures of Sponsor and CRO representatives can be found on the Signature Page.

10.1 **Approval Procedures**

Before the start of the study, the study protocol and/or other relevant documents will be approved by the appropriate Ethics Committee.

The relevant authorities, in accordance with local legal requirements will be notified/asked for approval of the intended study.

10.2 **Protocol Amendments**

After initiation of the study, any change in this protocol will require a formal amendment. The amendment must be signed by all of the signatories to the original protocol. Once the study has started, amendments will be made only in exceptional cases.

If ethically relevant aspects are concerned, the Ethics Committee(s) will be informed of amendments and approval will be sought.

All protocol amendments will be submitted to the regulatory authorities as regulated by national law.

Changes to the protocol may only be implemented after all appropriate requirements listed above (ethics, regulatory approval of all responsible personnel) have been fulfilled.

